## 1 Table of Contents

1	Table of Contents	2
2	Administrative Information	4
3	Introduction	6
3.1	Background	6
3.2	Aim of the Study	8
3.3	Study Hypothesis and Objectives	8
3.3.1	Hypothesis	8
3.3.2	Primary Objective	8
3.3.3	Secondary Objectives	8
3.4	Trial Design	9
3.4.1	Post Traumatic Headache Education Study Flow Diagram	9
3.5	Methods: Participants, Measures and Outcomes	10
3.5.1	Eligibility Criteria	10
3.5.2	Interventions	10
3.5.3	Outcomes	13
3.5.4	Primary Outcome Measures	13
3.5.5	Secondary Outcome Measures	13
3.5.6	Sample Size	14
3.5.7	Recruitment	14
3.6	Methods: Assignment of Intervention	14
3.6.1	Allocation	14
3.6.2	Blinding	14
3.7	Methods: Data collection, management and analysis	15
3.7.1	Data Collection	15
3.7.2	Primary Outcomes.	16
3.7.3	Secondary Outcomes	17
3.7.4	Retention	18
3.7.5	Data Management	18
3.7.6	Statistics	18
3.8	Ethics and dissemination	18
3.8.1	Ethics	18
3.8.2	Study participants' identification	19
3.9	Appendices	19
3.10	References	19

Lists of abbreviations and terminology

mTBI: Mild Traumatic Brain Injury  
PTH: Post Traumatic Headache  
RPQ: Rivermead post-concussion questionnaire  
PART-O: Participation Assessment with Recombined Tools-Objective  
QOLIBRI: Quality of Life after Brain Injury  
REDCap: Research Electronic Data Capture

Protocol Summary:

*Full Title:* Can targeted education impact the current standard of care in patients with mild traumatic brain injury?

*Sample Size:* Approximately 70 patients

*Study Population:* Patients seen at the St. Michael's Head Injury Clinic

*Study Design:* Randomized-Control Study

*Study Duration:* January 2018- December 2019

*Study Agent/ Intervention/ Procedure:* Educational

*Primary Objective:* Are we able to see a decrease in patients reported symptoms by 3 on the Rivermead post concussion questionnaire or RPQ-3 and 10 on the RPQ-13 in those that receive targeted headache education in comparison to those who do not?

*Secondary Objectives:* When and what type of health care services do participants in this study access, how frequently and is there a difference and between the two groups.

Does education through reinforcement of appropriate lifestyle and treatment strategies translate to similar pre-injury scores on the PART-O tool at the 12-week time point.

By the end of the study, the educational intervention group will be more satisfied in various aspects of their life as measured by the QOLIBRI compared to their week 0 scores.

*Endpoints of the study:* Significance will be observed if patients reported symptoms decrease by 3 points on the RPQ-3 and 10 on the RPQ-13.

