##### **3.3.3.2 Other Secondary Objectives**

- Does education through reinforcement of appropriate lifestyle and treatment strategies translate to similar pre-injury scores on the PART-0 tool at the 12-week time point.
- By the end of the study, the educational intervention group will be more satisfied in various aspects of their life as measured by the QUOLIBRI compared to their week 0 scores.

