### **3.5.2.5 Concomitant Care**

All patients will be seen in a tertiary level clinic. Clinicians are blinded to the allocation of the study participants. Therefore, regardless of their study allotment they will receive the current standard of care provided in the clinic.

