#### **3.5.5 Secondary Outcome Measures**

For the secondary endpoints, we will analyze the frequency and type of health care patients accessed outside of their current standard of care during the 12-week study period. This will be compared to our controls and will include emergency room, family physician visits, hospital admissions and telehealth that are related to post traumatic headache symptoms.

Another end point we are interested in exploring is whether patients that are provided targeted headache education along with tertiary care has an increased frequency of social interactions in comparison to patients receiving the current standard of care. We are very interested in the hours that each patient devotes to their previous work or hobbies and we will be comparing this once again to patients in the clinic who are receiving the standard of care. This outcome will be measured using the PART-0 tool which asks questions about the type and frequency of social engagements that patients may encounter each week along with the hours that patients devote to returning back to work, school or homemaking.

Lastly, we are interested in whether or not education and reassurance alter a patient's perceived quality of life after a mild-traumatic brain injury. This will be analyzed by using the QOLIBRI (Quality of Life after Brain Injury). Using this scale we hope to capture whether or not patients believe they play an active role in their health and whether or not they feel empowered to alter their health status. It will hopefully also allow us to capture what

barriers there are to a patient's recovery in regard to what negative feelings and limits they perceive; preventing them from making a meaningful recovery.

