### **3.7 Methods: Data collection, management and analysis**

#### **3.7.1 Data Collection**

For all visits each patient will fill out a questionnaire (See Appendices for full surveys) using RedCap. If a patient is unable to enter the data using email directly, one of our research assistants will enter the data into the RedCap system via telephone interview. For the follow up survey if there is no response, we will attempt to contact the patient by phone three times. In regard to those patients seen in follow up in the clinic, we will ensure that they finish their follow up questionnaires after being seen by a healthcare professional to avoid unblinding. Patients' receiving the standard of care will be asked the same questions at week 0 and 12 with the same surveys as the education intervention arm of the study. A secure password protected master linking log will be able to house the patient name with study identification number.

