#### **3.7.7 Statistics**

The IBM SPSS statistical software will be used for the data analysis. Data will be entered on demographic factors (sex, age, ethnicity, years of education), frequency and type of health care accessed will be analyzed as well. Scores on the Rivermead, PART-O and QUOLIBRI will be analyzed and comparisons will be made between the educational arm and the current standard of care group. We will be using univariate Chi-square analysis for categorical variables and 1 way analysis for continuous variables to assess for significant difference. P-value of <0.05 will be considered as statistically significant.

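### The QOLIBRI objective compares the education arm with its own week-0 scores, whereas Section 3.7.7 compares QOLIBRI between the arms; the objective should be reworded to match.

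*Protocol*

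**What the plan says.** The objective appears twice. The Protocol Summary sets the education group's satisfaction "as measured by the QOLIBRI compared to their week 0 scores". Section 3.3.3.2 repeats it: "the educational intervention group will be more satisfied in various aspects of their life as measured by the QUOLIBRI", again measured against that group's own week-0 scores. Neither place mentions the control arm.

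Section 3.7.7 on statistics takes the other view. It groups QOLIBRI with the Rivermead and PART-O scores and states that "comparisons will be made between the educational arm and the current standard of care group".

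Section 3.5.5 asks, for QOLIBRI, "whether or not education and reassurance alter" the patient's perceived quality of life. That is a causal question, but no comparator is named. The two outcomes described just before it, health-care use and PART-O, are both set against controls or standard-of-care patients.

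The control data will exist. Section 3.7.1 says that patients "receiving the standard of care will be asked the same questions at week 0 and 12", using the same surveys as the education arm. Section 3.5.2.5 adds that "regardless of their study allotment they will receive the current standard of care provided in the clinic".

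**The concern.** An objective states the question that the analysis must answer. This one would be satisfied by the education arm improving on its own baseline, whatever happens in the control arm. Both arms attend the same tertiary clinic for the 12 weeks, so any benefit of that care, any further recovery and any effect of answering the questionnaire a second time would all appear in the within-arm change. None of these can be separated from the education without the control arm. Section 3.4 justifies the randomised design as the way to establish cause and effect, and a before-after comparison gives up that advantage.

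The conflict also leaves open which statement governs. A later analysis could follow the objective or Section 3.7.7 and claim in either case to follow the protocol.

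**Working it through.** **The protocol's own figure.** There is none to reproduce. The protocol gives no effect size, SD or power for QOLIBRI.

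**The texts side by side.**
- Protocol Summary and 3.3.3.2: education arm at the end of the study against education arm at week 0.
- 3.7.7: education arm against standard-of-care arm.
- 3.7.1: both arms surveyed at weeks 0 and 12, so either comparison is feasible.

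Let the education arm's mean change be c + δ and the control arm's be c, where c is the change common to both arms and δ the education effect. The objective as worded looks at c + δ. The comparison in 3.7.7 looks at (c + δ) − c = δ. They agree only if c = 0.

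**Size of the discrepancy if the objective were tested as worded.** Inputs from Section 3.5.6: 28 completers per arm (35 enrolled, since 28 / 0.80 = 35) and two-sided alpha 0.05. Assumptions: δ = 0, and c between 0.1 and 0.5 SD of the change score.

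The paired t statistic has 27 degrees of freedom, critical value 2.052 and noncentrality (c/SD) × √28 = 5.29 × (c/SD). The probability of a significant improvement is the noncentral-t probability above 2.052:

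| Common change, SD of change | Noncentrality | Significant improvement, no education effect |
|---|---|---|
| 0 | 0 | 2.5% |
| 0.1 | 0.53 | 7.4% |
| 0.2 | 1.06 | 17.4% |
| 0.3 | 1.59 | 33.4% |
| 0.4 | 2.12 | 53.2% |
| 0.5 | 2.65 | 72.3% |

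**Sensitivity.** If c is expressed in SDs of the week-0 score, the SD of change is √(2(1 − ρ)) of that SD, where ρ is the correlation between weeks 0 and 12. At ρ = 0.5 this equals 1 and the table is unchanged. At ρ = 0.7 it is √0.6 = 0.775, and the range for 0.1 to 0.5 SD becomes 9.7% to 90.9%. If all 35 enrolled patients complete, at ρ = 0.5 the range is 8.3% to 82.0%.

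**The comparison in 3.7.7 under the same conditions.** In 20,000 simulated trials per setting (28 per arm, no education effect, common change of 0, 0.2, 0.3 or 0.5 week-0 SD, ρ of 0.5 or 0.7), t tests between arms on the change score and on the week-12 score were significant in 4.8% to 5.3% of trials, two-sided. The common change cancels, as the algebra shows.

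**The case against.** The strongest reply is that the protocol never plans the faulty test. The only analysis stated for QOLIBRI is the between-arm one in 3.7.7, and no paired or within-arm test appears anywhere. Section 3.2 also says that the study compares two groups and lists perceived quality of life among its endpoints. The objective itself is an expectation: unlike the RPQ statement, it carries no threshold and no decision rule. This stands. A reader might infer that the trial will credit natural recovery or regression to the mean to the education, but the documents do not support that, because following 3.7.7 removes any common change.

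The size of the common change is also open to doubt. Patients enter at least 12 weeks after injury (3.5.7), and the background cites persistently high symptom scores despite treatment in patients six months or more after injury. Selection is on an RPQ score of 3 or more (3.5.1.1), a low cut-off on a different instrument, so regression to the mean in QOLIBRI has only a weak basis. This stands too: improvement in both arms is plausible, but the documents do not show that it should be expected. It is why the illustration starts at 0.1 SD.

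Finally, baseline adjustment and the handling of within-arm change are details often left to an analysis plan. That is fair. The comparator named in the objective is not such a detail, and here it is stated in a way that the same protocol contradicts.

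**Conclusion.** The point holds as an inconsistency. The QOLIBRI objective, in both places, is a within-arm comparison that cannot attribute change to education and that contradicts the between-arm analysis in 3.7.7. The protocol does not say which governs.

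The consequence is conditional. Only if success were judged on the objective's wording would the chance of a false claim of benefit rise from 2.5% to somewhere between about 7% and 72%. That range rests on 28 completers, no education effect and an assumed common improvement of 0.1 to 0.5 SD of the change score; the protocol supplies no QOLIBRI figure to narrow it. Under 3.7.7 the error rate stays near 5% two-sided.

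The issue is modest. It concerns one of the other secondary objectives and touches neither the sample size nor the conduct of the trial. It should still be corrected, because the wording determines what the trial may conclude about quality of life.

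**What to change.** Reword the objective in the Protocol Summary and in 3.3.3.2 to agree with 3.7.7: week-12 QOLIBRI will be higher in the education arm than in the standard-of-care arm, adjusted for week-0 QOLIBRI. Name the same comparator in the QOLIBRI paragraph of 3.5.5. Report change from week 0 within each arm descriptively, without a test and without a claim about the education.

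The essential change is the comparator. The week-0 adjustment is recommended because the score is already collected in both arms. The cost is a change of wording only, with no new data, visits or patients.

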### **3 Introduction**

#### **3.1 Background**

According to Chen et al. (2002), the annual medical costs of patients hospitalized with a traumatic brain injury in Ontario in the first follow-up year were approximately \$120.7 million between 2004 and 2007. Preventable injuries cost the Canadian economy \$27 billion per year, with more than 3.5 million emergency room visits and without intervention by 2035 will cost \$75 billion per year. Acute care cost accounted for 46-65% of the total treatment cost in the first year overwhelming all other cost components. Traumatic brain injuries is an expensive neurological disorder; the most common type of brain injury health care providers will encounter in the outpatient setting is mild traumatic brain injury. We define mild traumatic brain injury (mTBI) as a physiological disruption of brain function, manifested by any period of loss of consciousness, loss of memory for events immediately before or after the accident, alteration in mental state at the time of the accident and focal neurological deficit(s) that may or may not be transient. The severity of the injury cannot exceed a loss of consciousness of greater than 30 minutes, a Glasgow Coma Scale (GCS) no less than 13–15; 30 minutes post injury and posttraumatic amnesia (PTA) not greater than 24 hours. Although many patients with mTBI have rapid symptom resolution, there is a specific subgroup of patients referred to as the “miserable minority” who experience chronic symptoms that present as a therapeutic challenge. Unfortunately, there has been much discussion and great controversy surrounding the mere existence of a “post-concussive syndrome,” with comparatively less attention being paid to development of effective treatments for affected individuals

Clinical and research findings suggest 4 main symptom constellations comprising the clinical presentation of chronic mTBI concussive syndrome: (1) cognitive symptoms, including reduced attention, mental control, executive dysfunction, and recall deficits secondary to reduced attention; (2) physical symptoms, such as headache, sensory changes, and cognitive/physical fatigue; (3) psychiatric sequelae, including depression, anxiety, and posttraumatic stress disorder; and (4) emotional dysregulation. Of the many manifestations of post concussive syndrome listed above, headache is an integral and consistently endorsed symptom in this patient population. It is often the symptoms that is managed and understood the most poorly. Therefore, it seemed fitting that for this study post traumatic headache would be the symptom to analyze. At times, it can be difficult to classify headache, however the current standard is to use the definition set by the International classification of Headache disorders third edition-beta (ICHD-3). Post traumatic headache is defined as a secondary headache disorder in which the headache is reported to have developed within 7 days after either an injury to the head, regaining of consciousness following the injury to the head or discontinuation of medication(s) that impair ability to sense or report headache following the injury to the head. An acute headache is classified as lasting 3 months with the definition shifting to persistent if the headache is present after this time period. When not properly managed post traumatic headache can severely lengthen the time patients take to return to their baseline functioning if ever. Because of their protracted course this patient population has a greater

tendency to access health care resources. We know that among prevalent cases with traumatic brain injury aged younger than 65 years, the majority of the costs associated with health system use were attributable to hospital care (46.0%), physician and other health care professional services (27.8%) and prescription drugs (10.1%). The obvious goal is to reduce the burden on the healthcare system, empower patients to make informed healthcare decisions, facilitate return to the workforce and to improve quality of life after injury.

In a preliminary study by Kirkham et al. (2016) their group found that despite treatment directed at headache, depression and fatigue, patients who were at least 6 months out from injury had persistent high scores on the Rivermead post-concussion symptoms questionnaire along with high scores on the fatigue severity scale and the patient health questionnaire. Education surrounding head injury is not standardized and remains inconsistent. Much of the literature surrounds the pediatric population pertaining to sport related injuries. There is a large knowledge gap in the adult population who arrive to the ER after a mild traumatic brain injury and in the same subset of patients who present later on into the chronic phase of their symptoms. We aim to build upon Kirkham's work with the idea that if we can empower and educate patients, their anxiety levels will become less of a confounder on recovery. We will also be looking at level of activity and severity of headache i.e. is the level of the headache the same but the level of activity higher. Previous studies have attempted to show that early educational information in the form of expectation management is a means for reducing long-term mTBI symptoms. The CDC recommends monitoring symptoms and intervening in the acute stage (less than 3 months) to ensure the best possible outcome. Typically, psychoeducational treatment consists of the early provision of information related to the mild TBI diagnosis and possible symptoms, normalization of symptoms, reassurance of positive expectation of recovery, and education on coping strategies. A RCT completed by Wade et al. showed that when individuals receive early routine follow-up that included education plus targeted interventions, patients experienced significantly less disruption of social and functional ability and fewer or less severe post concussive symptoms than individuals receiving usual hospital services.

Based on these studies, the question remains as to how best consistently treat this unique patient population. We know that many mTBI patients are not consistently being referred to a specialized clinic directly from the ER and of those patients they may present months later to their primary care providers, walk-in clinics or the ER after their symptoms persist. Our goal is to set in place a standard of care that will decrease symptom reporting and improve functional outcomes, starting with a patient population that is already being provided a multi-disciplinary care approach. Allowing the patient to experience improved self-efficacy with appropriate levels of expectations and perceived improvement in quality of life. We also hope to show that we can reduce the number of health care related visits (ER, Walk-in clinics etc.) that patients with post-traumatic headache will access in comparison to the current standard of care. Future goals will include using this approach to assess other post concussive symptoms in the multi-disciplinary clinic along with developing educational material that provides a clear and consistent message when treating head injury patients. We would also like to expand this education model to different clinic settings in order to provide this level of care to patients more acutely and ultimately reduce wait times for subspecialty clinics.

Grant 17-0098-GAP, REB 17 227

Version Date: April 16, 2019

### **3.2 Aim of the Study**

The aim of the study is to ask the question as to whether or not targeted education will decrease symptom reporting in those suffering from post-traumatic headache after mild traumatic brain injury. The primary endpoints being measured include symptom reporting, perceived improvement in quality of life, utilization of health care services and return to baseline level of functioning.

This study will compare two groups of patients that are in the chronic phase (12 weeks and on) of their post-traumatic headache symptoms.

This model of educational intervention aims to change the way we deliver education material to this specific subset of patients. The goal is to apply this method of education to individuals with other mild-traumatic brain injury symptoms that can be realistically provided in a primary health care setting, ultimately reducing wait times for subspecialty clinics. Questions asked throughout the study will be provided by common data elements that will be used not only to standardize the study but to promote further research in the field across multiple sites in the province.

### **3.3 Study Hypothesis and Objectives**

#### **3.3.1 Hypothesis**

Providing targeted education headache education to patients who have suffered from mild traumatic brain injury will reduce symptom scoring on the Rivermead Concussion Questionnaire by week 12 of the study.

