#### **3.3.2 Primary Objective**

Are we able to see a decrease patient reported symptoms by 3 on the Rivermead post-concussion questionnaire or RPQ-3 and 10 on the RPQ-13 in those that receive targeted headache education in comparison to those who do not?

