### **3.5.3 Outcomes**

#### **3.5.4 Primary Outcome Measures**

Targeted education provided to patients suffering from post-traumatic headache will be assessed using the RPQ. The RPCSQ is a 16-question instrument that examines post-concussion symptoms rated by the patient according to the increase in their frequency compared with premorbid levels. The total score is calculated based on 2 domains (cognitive and emotional-somatic) and ranges from 0 to 72. The RPQ has been shown to measure severity of postconcussion symptoms reliably with good test-retest and inter-rater reliability for individual symptom scores. Based on previous studies, splitting the RPQ into two subscale scores: RPQ-3 uses the sum of scores from three items (headaches, dizziness and nausea) and RPQ-13 uses the sum of scores of the other 13 items. Higher scores especially for the RPQ-13 subscale are associated with greater impact on lifestyle. For our study significance will be observed if patients reported symptoms decreased by 3 on the RPQ-3 and 10 on the RPQ-13.

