### ***3.7.3 Primary Outcomes.***

Data will be collected using the Rivermead Post Concussion Symptoms Questionnaire (RPQ): The symptoms listed on the RPQ are those most commonly reported in the published literature as post concussion syndrome (PCS). The RPCSQ is a 16-question instrument that examines post-concussion symptoms rated by the patient according to the increase in their frequency compared with premorbid levels. The total score is calculated based on 2 domains (cognitive and emotional-somatic) and ranges from 0 to 72. The RPQ has been shown to measure severity of postconcussion symptoms reliably with good test-retest and inter-rater reliability for individual symptom scores. Based on previous studies, splitting the RPQ into two subscale scores: RPQ-3 uses the sum of scores from three items

(headaches, dizziness and nausea) and RPQ-13 uses the sum of scores of the other 13 items. Higher scores especially for the RPQ-13 subscale are associated with greater impact on lifestyle. For our study significance will be observed if patients reported symptoms decreased by 3 on the RPQ-3 and 10 on the RPQ-13.

We will be comparing headache symptom reporting between the two groups assigning significance if patients in the education arm have a decrease in symptom reporting on the RPQ-3 by 3 and 10 on the RPQ-13.

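### RPQ-3 and RPQ-13 are the stated primary scores, but the point rule for significance and the P<0.05 rule are different tests, and no section says which one decides the trial

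*Protocol*

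**What the plan says.** - **Hypothesis (3.3.1).** Education "will reduce symptom scoring on the Rivermead Concussion Questionnaire by week 12 of the study". The instrument and time point are given, but no score.
- **Primary objective (3.3.2, repeated in the Protocol Summary).** A decrease "by 3 on the Rivermead post-concussion questionnaire or RPQ-3 and 10 on the RPQ-13", worded as a comparison with patients who do not receive the education.
- **Endpoints entry of the Protocol Summary, 3.5.4 and 3.7.3.** Each defines significance by the same two point decreases, again joined by *and*. Section 3.7.3 adds a sentence that opens as a comparison of the two groups but closes by "assigning significance if patients in the education arm have a decrease in symptom reporting on the RPQ-3 by 3 and 10 on the RPQ-13".
- **Total score.** Sections 3.5.4 and 3.7.3 also describe the whole instrument: "The total score is calculated based on 2 domains (cognitive and emotional-somatic) and ranges from 0 to 72". No section sets a criterion on that total.
- **Statistics (3.7.7).** "Scores on the Rivermead, PART-O and QUOLIBRI will be analyzed and comparisons will be made between the educational arm" and the standard-of-care group. The criterion is "P-value of <0.05 will be considered as statistically significant". The section does not say which Rivermead score is tested, or whether it is the week-12 value or the change.
- **Aim (3.2).** Four concepts are called primary: symptom reporting, quality of life, use of health services and return to baseline function. Sections 3.3.3 and 3.5.5 treat the last three as secondary.

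**The concern.** A primary analysis needs one rule that turns the data into a conclusion. Here the word significance has two meanings. In the outcome sections it is a number of points; in the statistics section it is a P-value. The point rule is itself worded as a between-arm contrast in 3.3.2 and as a decrease in the education arm in 3.7.3. Nothing carries the *and* between RPQ-3 and RPQ-13 into the test.

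The claim the trial may make is at stake. If the rules disagree on the observed data, the protocol does not say which prevails, and the choice could be made after the results are known. This goes beyond detail commonly left to an analysis plan, because the protocol's own definitions of success conflict.

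**Working it through.** **Inputs from the protocol.** Two-sided alpha 0.05, 80% power, 28 evaluable per arm and 20% attrition (3.5.6); point thresholds 3 and 10 (3.3.2, 3.5.4, 3.7.3). The attrition step reproduces: 28/0.8 = 35 per arm. The 28 is taken as given. It was derived from headache prevalence, so it does not show which RPQ contrast is primary.

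**Assumptions.** The protocol gives no SD and no correlation between the subscales. I use SD 3 for RPQ-3, SD 11 to 12 for RPQ-13, and correlations from 0 to 0.9.

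**Step 1: what P<0.05 requires.** The smallest significant difference is 1.96 × SD × √(2/28) = 0.524 SD.

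| Score | Assumed SD | Difference giving P<0.05 | Point rule |
|---|---|---|---|
| RPQ-3 | 3 | 1.6 | 3 |
| RPQ-13 | 11 | 5.8 | 10 |
| RPQ-13 | 12 | 6.3 | 10 |

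An observed difference between the last two columns is significant under 3.7.7 and fails the point rule. The order reverses only if the SD exceeds 3/0.524 = 5.7 (RPQ-3) or 10/0.524 = 19.1 (RPQ-13).

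**Step 2: how often the rules part.** Read the point rule as an observed between-arm difference and suppose the true difference equals the threshold. The observed difference then falls short in half of trials. Power for P<0.05 at 28 per arm is 96.3% (RPQ-3, SD 3), 92.5% (RPQ-13, SD 11) or 87.7% (RPQ-13, SD 12). The share of trials that are significant but miss the threshold is power minus 50%: about 46%, 43% and 38%.

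**Step 3: the within-arm reading.** If the closing words of 3.7.3 are taken literally, an education arm that falls by 3 and 10 points meets the rule even when the control arm falls by the same amounts. The protocol gives no expected control change, so I put no size on this.

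**Step 4: error rate under each joint rule (no true effect, two-sided 0.05 tests).**
- Either subscale enough: 1 − 0.95² = 9.75% at correlation 0, about 9.1% at 0.5 and about 8% at 0.8.
- Any of total, RPQ-3 or RPQ-13 enough: about 10.1% at correlation 0.3 and 8.5% at 0.7.
- Both subscales required: about 0.9% at correlation 0.5, and never above 5%, even if one subscale has a true effect.

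**Step 5: power if both are required.** With 80% on each subscale, joint power is 64% (correlation 0), 69% (0.5) and 75% (0.9). One subscale is significant without the other in 32%, 23% and 10% of trials. At 28 per arm, 80% on each corresponds to SDs of about 4.0 and 13.4. With smaller SDs the cost shrinks: at 3 and 11 and correlation 0, joint power is 0.963 × 0.925 = 89%.

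**The case against.** The strongest reply is that the protocol is consistent on the scores. Every statement of the endpoint names RPQ-3 and RPQ-13 and joins them with *and*. A general hypothesis followed by an operational objective is normal drafting. The naming of the questionnaire before RPQ-3 in 3.3.2 looks like an editing slip, since a 3-point target on the whole instrument beside a 10-point target on part of it would be odd. Which score enters the test, and any multiplicity rule, may stand in an analysis plan that is not shown.

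Most of this stands, and it rules out two stronger readings.

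- A reader might infer three rival primary outcomes: total, RPQ-3 and RPQ-13. The text does not support that. Section 3.3.1 does not mention a total, and the 0–72 sentence describes the instrument before the text moves to the subscales.
- A reader might infer a false-positive rate of about twice 0.05. That requires a rule that one significant score is enough, and no section states one. Nor does 3.7.7 say that 0.05 applies to each score separately.

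The reply does not remove the conflict between the definitions of significance. The *and* joins point decreases, not tests; 3.3.2 and 3.7.3 word those decreases differently; and 3.2 contradicts 3.3.3 on what is primary. An analysis plan could choose among these rules, but the protocol would still state the others.

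**Conclusion.** The point holds as a conflict over the success rule, not over which scores are primary. The protocol intends RPQ-3 and RPQ-13 together, but it does not turn that into one deciding test.

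The gap is material. At the assumed SDs, P<0.05 is reached at a little over half the required points (1.6 against 3; about 6 against 10). A true effect equal to the threshold would be significant yet miss the threshold in roughly 38–46% of trials on a given subscale. These sizes depend on the assumed SDs and on reading the thresholds as observed between-arm differences. The conflict in the text does not depend on them. The 8–10% error rate is conditional on a one-score-is-enough rule; under the stated *and* the rate is at most 5%. This should be corrected, and the correction is mainly a matter of text.

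**What to change.** 1. In 3.7.7, define the primary analysis as the between-arm comparison at week 12 on RPQ-3 and on RPQ-13, each at two-sided 0.05, with success only if both are significant in favour of education. No alpha split is needed.
2. In the Protocol Summary, 3.5.4 and 3.7.3, present 3 and 10 points as the target between-arm differences used to judge the size of effect, not as the definition of significance.
3. Align 3.3.1 with 3.3.2, remove the reference to the whole questionnaire that precedes RPQ-3 in the objective (also in the Summary), and label the RPQ total supportive.
4. In 3.2, call only the RPQ outcome primary, in line with 3.3.3.

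**Cost.** No new data or patients are needed, but step 2 changes the stated success rule and should be recorded as such. One subscale or the total alone could no longer be claimed as success. Joint power is about 64–75% if each subscale has 80%, and the protocol should say so. If the sponsor prefers that either subscale suffice, testing each at 0.025 raises the requirement at an RPQ-3 SD of 4.0 from 28 to 34 per arm, or 34/0.8 = 43 enrolled.

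This version is dated April 2019, after the recruitment period planned in 3.5.7 (January to December 2018). The change should therefore be dated and made before anyone on the study team sees outcomes by arm.
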